Descriptive statistics will be generated for radiation exposure and frequency of follow-up CT scans and other nodule-related resource utilization will be obtained by site and study arm. For each type of nodule-related resource utilization, we will also create a binary variable to indicate whether a patient has any exam of that type (1 yes and 0 no) and obtain the corresponding frequency. For H3a, to examine whether among all participants with a lung nodule ≤ 15 mm, more intensive surveillance will be associated with a greater number of specific follow-up tests and types of follow-up tests (e.g., imaging, non-surgical biopsy, surgery), we will use mixed-effects Poisson regression model including random site effects to account for clustering of patients within sites. We will also model the frequency at which at least 1 specific follow-up test or type of follow-up test is performed using hierarchical logistic regression that includes random site effects. All regression models mentioned above will be fitted with and without potential confounders including age, gender, ethnicity/race, smoking, BMI, nodule size, and any facility-level factors balanced during the randomization. For H3b, to examine whether among all participants with a lung nodule ≤ 15 mm, more intensive surveillance will be associated with a greater number of serious complications related to invasive procedures, similar strategy used for H3a will be adopted. We will model the number of serious procedure-related complications using mixed-effects Poisson regression models and the frequency of patients with any serious complications using hierarchical logistic regression models. For H3c, to investigate whether all participants with a lung nodule ≤ 15 mm, more intensive surveillance will be associated with greater total exposure to diagnostic radiation than less intensive surveillance, we will use mixed effects models and log-transform the radiation exposure to make normal assumption more appropriate.

For H4, binary variables will be generated to indicate adherence to the recommended protocols measured at the level of the ordering provider and the patient. Cross tabulations of the

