adherence indicators and the surveillance arm will be obtained. To examine whether among all participants with a lung nodule ≤ 15 mm, more intensive surveillance will be associated with worse adherence to the surveillance protocol than less intensive surveillance, we will use hierarchical logistic regression that includes random site effects, with and without adjusting for potential confounders including age, gender, ethnicity/race, smoking, BMI, nodule size, and any facility-level factors balanced during the randomization.

Sample size and power calculations by aim

Preliminary data from a retrospective study of patients who underwent one or more chest CT scans at KPSC (2006-2012) showed that 76% of chest CT scans are performed in unique patients, and that approximately 30% of these individuals will have a prior history of cancer. Of the remainder, approximately 32% of unique patients (with no prior cancer diagnosis) who undergo chest CT will have a pulmonary nodule ≤ 30 mm, and 72% of all nodules measure ≤ 15 mm. Thus, we expect that approximately 16% of all unique patients who undergo chest CT will have a qualifying pulmonary nodule measuring ≤ 15 mm and no prior history of cancer. Data provided by participating sites indicates that more than 376,000 chest CT scans will be performed during the planned 20-month enrollment period in over 279,500 unique individuals (**Table 1**). This translates to an estimated target population size of approximately 45,000 patients with qualifying nodules. Allowing for site-level variation in the proportion of patients with a prior history of cancer and patients with nodules detected on prior chest CT scans, we will passively enroll a minimum of 35,200 individuals with a nodule ≤ 15 mm at one of the 14 health systems (24 individual study sites for cluster randomization) during the initial 28-month recruitment period. To allow time to complete the evaluation and accrue outcomes, patients will be followed for at least 2 years during the funding period. Among these individuals with small pulmonary nodules, we assume (based on data from KPSC) that 3.0% will be diagnosed with lung cancer, resulting in a sample size of approximately 1,056 patients with cancerous nodules.

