Aim 3: The primary outcome for this aim is the total number of non-invasive and invasive procedures performed from the date of the index CT scan to the end of surveillance. We assume that patients who undergo more intensive surveillance will have 3.5 procedures on average. A sample size of 32,000 individuals with small nodules provides 90% power to detect a difference of 0.14 standard deviations for this outcome, assuming a two-sided alpha of 0.05 and an ICC of 0.01.

We will also compare the frequency of invasive testing among individuals with benign nodules. Based on data from the NLST, we assume that 5% of patients with benign nodules will undergo at least one invasive test. With an estimated sample size of 15,520 individuals with benign nodules in each group, and assuming a 2-sided alpha level of 0.05 and an ICC of 0.01, we will have 90% power to detect a difference between groups in the use of invasive testing of 3.4 percentage points.

Aim 4: For the analysis of radiologist adherence to inclusion of the recommendation for surveillance per protocol in the radiology report, we assume that radiologists will adhere to the assigned protocol for at least 85% of participants in the more intensive group. We estimated the ICC to be 0.19 based on preliminary data on radiologist variability in number of enrolled patients at the KPSC facilities. Assuming a 2-sided alpha of 0.05, we need to review at least 130 reports for enrolled patients at each participating facility to achieve 80% power to detect an improvement in adherence of 5.0 percentage points.

For the analysis of ordering physician adherence with ordering the surveillance test according to the assigned protocol, we assume that 80% of physicians in the more intensive group will be adherent. Assuming a 2-sided alpha of 0.05, our sample size of 16,000 individuals with small nodules in each group will provide >90% power to detect an improvement in adherence of 5.3 percentage points, assuming an ICC of 0.01-0.19.

For the analysis of patient overall adherence with surveillance, we assume that 27% of participants in the more intensive group will be non-adherent, based on the results of our study of guideline-concordant follow-up in veterans with pulmonary nodules.²⁴ Assuming a 2-sided alpha of 0.05, our sample size of 16,000 individuals with small nodules in each group will provide 90% power to detect an improvement in non-adherence of 5.9 percentage points, assuming an ICC of 0.01.

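### Ordering-physician adherence: the stated >90% power up to an ICC of 0.19 holds, under the site-effects model, only near a site ICC of 0.01, and the level of the 0.19 is not given

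*Combined protocol and SAP*

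**What the plan says.** All references are to the combined protocol and SAP.

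- **Sample size and power calculations by aim, Aim 4, ordering physicians.** The more intensive arm is assumed to be 80% adherent. With 16,000 patients per group and two-sided alpha 0.05, the sample "will provide >90% power to detect an improvement in adherence of 5.3 percentage points, assuming an ICC of 0.01-0.19".
- **Same section, radiologists.** Adherence in the more intensive arm is taken as at least 85%, with a 5.0-point improvement to be detected. On clustering: "We estimated the ICC to be 0.19 based on preliminary data on radiologist variability in number of enrolled patients at the KPSC facilities". On sample size: "we need to review at least 130 reports for enrolled patients at each participating facility to achieve 80% power".
- **Same section, neighbouring statements.** The Aim 3 procedure count is powered for "a difference of 0.14 standard deviations for this outcome, assuming a two-sided alpha of 0.05 and an ICC of 0.01". Patient adherence is said to "provide 90% power to detect an improvement in non-adherence of 5.9 percentage points, assuming an ICC of 0.01".
- **Number of clusters.** The opening of the section gives "24 individual study sites for cluster randomization".
- **Analysis Plan, H4.** The model is "hierarchical logistic regression that includes random site effects, with and without adjusting for potential confounders". The outcome variables are described as follows: "binary variables will be generated to indicate adherence to the recommended protocols measured at the level of the ordering provider and the patient". Hypothesis H4 itself names three levels: interpreting radiologist, ordering provider and patient.

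**The concern.** In a cluster-randomized trial with 24 sites, power is limited mainly by the number of sites once the site ICC is more than very small. A claim that power stays above 90% while the ICC rises from 0.01 to 0.19, a nineteen-fold range, cannot hold if the ICC is at site level. A reader would take the sentence to mean that the ordering-physician comparison is safe even under strong clustering, and could then read a null result as well powered.

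The 0.19 has two further problems. Its level (site, radiologist or provider) is not named, and the power depends heavily on which it is. It was also estimated from the number of patients enrolled, not from adherence, which is the outcome being powered. The section on primary endpoints lists adherence by radiologist, physician and patient under Aim 4, so these are not incidental figures.

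**Working it through.** **Inputs.** From the plan: two-sided alpha 0.05; physicians 80% vs 85.3%, n = 16,000 per arm; radiologists 85% vs 90%, 130 reports per facility; 24 sites. Assumed, because the plan does not say: 12 sites per arm of equal size. This gives m = 16,000/12 = 1,333 patients per site, and 130 × 12 = 1,560 reports per arm.

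**Formulas.** Site-level clustering: DE = 1 + (m − 1) × ICC and n_eff = n/DE. Power = Φ(d/SE − 1.96), with SE = √[(p1(1 − p1) + p2(1 − p2))/n_eff].

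**1. Does this method reproduce the plan's ICC 0.01 figures?**

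| Statement | Stated | Site ICC 0.01 |
|---|---|---|
| Aim 2, 0.22 SD, 792 per arm | >90% | 92.6% |
| Aim 3 procedures, 0.14 SD | 90% | 91.1% |
| Aim 3 invasive testing, 5% vs 8.4%, 15,520 per arm | 90% | 89.6% |
| Aim 4 patient non-adherence, 27% vs 21.1% | 90% | 90.5% |

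It does, so these figures are consistent with a site-level ICC.

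**2. Ordering physicians, site-level ICC.** At 0.01: DE = 1 + 1,332.3 × 0.01 = 14.32; n_eff = 1,117; SE = √(0.2854/1,117) = 0.0160; 0.053/0.0160 = 3.316; power = Φ(1.356) = 91.2%. The lower end of the range reproduces. Moving up the range:

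| Site ICC | DE | n_eff per arm | Power, normal | Power, t with 22 df |
|---|---|---|---|---|
| 0.01 | 14.32 | 1,117 | 91.2% | 88.6% |
| 0.0105 | 14.99 | 1,067 | 90.0% | 87.2% |
| 0.02 | 27.65 | 579 | 66.5% | 62.6% |
| 0.05 | 67.62 | 237 | 33.2% | 30.9% |
| 0.19 | 254.1 | 63 | 12.0% | 11.4% |

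Power of 90% is lost at a site ICC of about 0.0105 (normal) or 0.0095 (t). At 0.19, n_eff cannot exceed 12/0.19 = 63 per arm however many patients are enrolled. A beta-binomial simulation (20,000 runs, t test on site means) gives 88, 63, 31 and 12% at 0.01, 0.02, 0.05 and 0.19.

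**3. Sensitivity to the assumptions.** An 11:13 or 13:11 split gives 90.8–91.3% at 0.01 and 11.9–12.1% at 0.19, so the split matters little. Unequal site sizes lower power: with an assumed coefficient of variation of 0.4 in site size, DE at ICC 0.01 is 1 + (1.16 × 1,333 − 1) × 0.01 = 16.5 and power is 87%.

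**4. If 0.19 is provider-level.** With k patients per provider, DE = 1 + (k − 1) × 0.19 + (1,333 − k) × ICC_site. Power stays above 90% up to about k = 74, 54 or 40 at an assumed site ICC of 0, 0.003 or 0.005. At a site ICC of 0.01 it does so only up to about k = 4 (90.2% at 4, 89.9% at 5).

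**5. Radiologists.** With a plain site ICC of 0.01: DE = 1 + 129 × 0.01 = 2.29; n_eff = 681; SE = √(0.2175/681) = 0.0179; power = Φ(2.798 − 1.96) = 79.9%, which matches the stated 80%. With 0.19 at site level: DE = 25.51, n_eff = 61, power about 13%. With 0.19 at radiologist level and k reports per radiologist, DE = 1 + (k − 1) × 0.19 + (130 − k) × ICC_site. The values of k and site ICC below are illustrative, since the plan gives neither:

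| Site ICC | k = 2 | k = 5 | k = 10 |
|---|---|---|---|
| 0 | 97% | 89% | 73% |
| 0.003 | 92% | 83% | 68% |
| 0.005 | 88% | 78% | 64% |
| 0.01 | 77% | 68% | 57% |

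**The case against.** The strongest defence is that 0.19 was never meant as a site ICC. It is introduced through variability between radiologists, which points to clinician level, and on a provider-level reading the >90% claim can be true (step 4). This stands as far as it goes: the failure at the upper end is conditional on a site-level ICC, and a reader who concluded that the physician comparison simply has 12% power would be going beyond the text. But the defence needs a level and a cluster size that the plan does not state, and a provider effect that the H4 model does not contain.

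A reader might also infer that the radiologist comparison has only 13% power. The documents do not support that. They do not say that 0.19 is between sites, and the 130 reports match 80% at a site ICC of 0.01, so it is not even clear that 0.19 was used in that calculation.

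Nor is a model for radiologist adherence wholly missing. The Aim 4 Outcomes section says how it is measured from sampled transcripts, and the H4 regression sentence excludes no level. The gap is that the list of indicator variables names only provider and patient.

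Finally, no sample size rests on the physician sentence, because 16,000 per group follows from total enrolment. That limits the consequence to how the result is read; it does not make the sentence correct.

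**Conclusion.** The concern holds in a conditional form. Under the only H4 model stated, and assuming 12 equal-sized sites per arm, the physician claim is supported at about a site ICC of 0.01 (89–91%) and not over the rest of the stated range, where power falls to about two thirds at 0.02 and 11–12% at 0.19. The 90% limit of 0.0095–0.0105 is on the favourable side, since unequal site sizes would lower it. If 0.19 is provider-level the claim may be right, but it cannot be verified from the plan.

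For radiologists, the plan presents an enrolment-count ICC of 0.19 beside a power figure that a site ICC of 0.01 reproduces. Which value was used, and at what level, is open; the radiologist power is unverified, not shown to be wrong.

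The point concerns the physician and radiologist power statements and one list of indicators. The Aim 1 and patient-adherence power calculations do not use the 0.19 and are not affected.

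**What to change.** 1. In the ordering-physician sentence, replace the ICC range with power at stated site ICCs: about 89–91% at 0.01, 63–67% at 0.02, 31–33% at 0.05 and 11–12% at 0.19. Describe the power as about 90% at a site ICC of 0.01, not above 90% across a range.
2. State the level to which 0.19 applies and the cluster size behind it (patients per provider, reports per radiologist). If it is provider- or radiologist-level, add that random effect nested within site to the H4 model and restate power with both variance components.
3. For radiologists, say which ICC yields 80% with 130 reports. If it is a site ICC of 0.01, say so; if 0.19 is intended, restate the power. State that the 0.19 describes enrolment counts, not adherence.
4. Add radiologist adherence to the H4 indicator list, so that the regression covers all three levels named in the hypothesis.

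The cost is protocol wording, one added indicator and possibly one more variance component, which may be poorly estimated where there are few reports per radiologist. No extra chart review is needed. The stated physician power becomes less favourable.

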Timeliness of treatment: To investigate whether among participants with cancerous nodules, less intensive surveillance will be non-inferior to more intensive surveillance for timeliness of treatment, we will restrict our analysis to participants with cancerous nodules and use Cox regression models where time from initial nodule identification to treatment is the outcome variable. Patients who die or do not receive treatment will be censored at end of follow-up. We will consider using competing risk models, as necessary.

H1c: Secondary endpoint

Survival: To investigate whether among participants with cancerous nodules, less intensive surveillance will be non-inferior to more intensive surveillance for overall survival, we will restrict our analysis to participants with cancerous nodules and use Cox regression models where time from initial nodule identification to death as the outcome variable. Patients will be censored at end of follow-up.

For all time-to-event analyses, clustering by site will be handled by specifying subjects nested within each cluster and using robust sandwich estimators for statistical inferences.⁶¹ The proportionality assumption will be checked by creating log-minus-log plots. To explore whether individuals who are most likely to benefit from more intensive surveillance, subgroup analyses will examine the effect of age (using the median and/or quartile values as cut points), nodule size (>8 mm), nodule attenuation (solid or part-solid nodules compared with non-solid nodules), and mode of detection (detected by screening compared with incidentally detected).

Analytically, we will include interaction terms between each of these factors with treatment in the models, respectively. For significant interactions, we will also conduct subgroup analysis to explore the treatment effects in corresponding subgroups. Since the study is not powered to test interaction terms, these analyses will be exploratory. For H1b, to study whether among participants with cancerous nodules, more intensive surveillance will result in more timely diagnosis and treatment than less intensive surveillance, we will adopt similar strategy used for comparing overall survival described above.

H2a:

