For H2b, to investigate whether among all participants with a lung nodule ≤ 15 mm, more intensive surveillance will be associated with scores similar to less intensive surveillance for general health status at 1-2 months, 13-24 months, and ≥ 25 months, a mixed effects model, including all subjects who complete at least two sets of surveys and the time variable as a categorical variable, and will allow the parameters corresponding to time trends to be random effects, so as to allow for between-subject heterogeneity in those trends. Formal tests of both between-site and between-subject heterogeneity will be used to rule out sources of clustering that are not warranted. The mixed effects models will be adjusted for potential confounders including age, gender, ethnicity/race, smoking, BMI, nodule size, and any facility-level factors balanced during the randomization. Interaction between the treatment assignment and time will also be considered in the models and subgroup analysis will be conducted at separate time points if the interaction term is significant. For H2c, to examine whether among participating radiologists and pulmonologists, satisfaction with the surveillance protocol will be greater among those who practice at institutions assigned to the less intensive protocol, similar analysis strategy for H2b will be adopted.

Similar methods will be used to evaluate ordering specialist, primary care, and radiologist knowledge attitudes and beliefs about existing guidelines for pulmonary nodule evaluation and provider satisfaction with the surveillance protocol and the evaluation process measured at approximately mid-way during follow-up.

Aim 3: Health care resource utilization and exposure to diagnostic radiation

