We will continue recruitment through the end of the study to collect additional data for HTE analyses with greater statistical power for Aim 1. We assume 10% loss to follow-up before final diagnosis is established based on KPSC membership data. This yields an estimated sample size for analyses of 960 individuals with cancerous nodules for Aim 1, and 32,000 individuals with small nodules for Aims 2-4.

Aim 1: For the primary outcome, the baseline risk of progression has not been reported. Conservatively, we assume that 5% of patients will progress from a tumor ≤ 15 mm to a tumor > 20 mm during the surveillance period. Assuming a two-sided alpha of 0.05, and an intraclass correlation coefficient (ICC) of 0.01, a sample size of 888 unique patients with cancerous lung nodules (444 per arm) is required to achieve 83% power to detect an absolute increase in tumor progression of 5 percentage points. Thus, our anticipated sample size of 960 unique patients with cancerous lung nodules provides adequate power to show non-inferiority of the less intensive surveillance strategy for our primary outcome of lung cancer stage $> T1a$ at diagnosis. The most uncertainty in our assumptions is for the ICC. We will have at least 80% power to detect a 5% increase in our primary outcome for ICC values of 0.012 or less. At the baseline ICC value of 0.01, a total sample size of 32,560 enrolled (including 888 patients with cancerous nodules) will have 0.83 power; for an ICC value of 0.012, a total sample size of 35,200 enrolled (960 patients with cancer) will also have 0.83 power.

Aim 2: Prior studies of anxiety and distress in lung cancer screening have shown that the identification of a lung nodule leads to anxiety and emotional distress that subsequently dissipates over 1-2 years.^{56 63 52} For our analyses of anxiety and emotional distress, we will have $> 90\%$ power to detect an effect size of 0.22 standard deviation, assuming an ICC of 0.01, even if the response rate is as low as 5%, resulting in an estimated sample size of approximately 792 respondents in each arm.

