Subgroup Analyses/Heterogeneity of Treatment Effect: During the 7.5-year study period, we will have sufficient power to achieve our primary aims based on the planned 28 months of enrollment. We limited the period of enrollment to enable follow-up of all enrolled patients for at least 2 years, to reliably exclude a diagnosis of cancer when absent, and to assess cancer outcomes when present. Analyses will include whether outcomes vary by CT indication (lung cancer screening or unrelated to lung cancer screening), lung cancer risk factors (primarily smoking history), nodule density (solid, part-solid or non-solid), health care setting, demographic characteristics, and geographic region. Each of these subgroup analyses will be guided by the clinically plausible, pre-specified hypothesis that more intensive surveillance is more effective in subgroups that are at higher risk for more aggressive forms of lung cancer, such as older individuals; smokers and former smokers; patients with screening-detected nodules, solid nodules, or nodules of larger size; and patients from regions where a large portion of nodules are caused by endemic fungal infections.

To examine differences in “treatment” effect, we will include relevant interaction terms in all regression models, and report magnitudes of effects and standard errors for each subgroup level when interactions are statistically significant.

[figure not shown]
Missing Data: Two types of missing data might occur: (1) core study variables (such as potential confounders) may be missing for some patients because of incomplete capture in the

EHR, and (2) patients might disenroll from a health system and/or leave the capture area. We will minimize missingness of core study variables through intensive quality assurance. The Data Coordinating Center will review monthly reports for potential data issues and follow-up with site coordinators and programmers to abstract missing data, correct data issues, and document in the study database when missing data cannot be found.

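### Subgroup effects are to be reported only when the interaction is significant, although the plan says it is not powered for interactions; modest Aim 1 interactions would be overstated and the remaining estimates not shown

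*Combined protocol and SAP*

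**What the plan says.** The Subgroup Analyses/Heterogeneity of Treatment Effect section sets a general rule in two parts. On modelling, it says "we will include relevant interaction terms in all regression models". On what is then shown, the investigators are to "report magnitudes of effects and standard errors for each subgroup level when interactions are statistically significant".

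Two parts of the Analysis Plan use the same condition. For Aim 1, under H1c: "For significant interactions, we will also conduct subgroup analysis to explore the treatment effects in corresponding subgroups". For H2b, where the interaction is treatment by time: "subgroup analysis will be conducted at separate time points if the interaction term is significant".

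The Aim 1 text adds: "Since the study is not powered to test interaction terms, these analyses will be exploratory". The sample size section mentions continued recruitment "to collect additional data for HTE analyses with greater statistical power for Aim 1", but gives neither a number of patients nor a power for any interaction.

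The effect modifiers and the expected direction are pre-specified. The pragmatic-trial scoring under Research Design and Methodology says that subgroups were chosen for their use in clinical decisions and not to find large effects. Nowhere do the documents promise subgroup estimates when the interaction is not significant.

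**The concern.** A significance condition on a low-powered test acts as a selection rule. If the threshold for significance lies above the true interaction, any estimate in the true direction that passes must exceed the truth. Estimates that fail are not promised to the reader at all.

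This works against the plan's own purpose. Aim 1 is a non-inferiority question, and a clinician deciding whom less intensive surveillance suits needs each subgroup's interval set against the 5-point difference used for power. That need is the same when the interaction test is negative, because a negative test with low power does not show that the effect is uniform. A rule that opens the subgroup results only after a positive test favours the large effects the plan says it is not looking for.

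**Working it through.** **Inputs from the sample size section.** 960 analysed cancers, 24 randomised sites, and a 5-point difference. Baseline risk: "we assume that 5% of patients will progress from a tumor ≤ 15 mm to a tumor > 20 mm during the surveillance period". Error rate and clustering: "Assuming a two-sided alpha of 0.05, and an intraclass correlation coefficient (ICC) of 0.01".

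**Assumptions, because the documents give no figure.** Subgroup share *f* among cancers of 10% to 50%; a true interaction δ of 5 points, then 10; the cell risks; and how far clustering inflates the interaction variance (D from 1 to 1.39).

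**Step 1. Reproduce the plan's own power.** With 888 cancers, D = 1 + (888/24 − 1) × 0.01 = 1.36, so 444/1.36 = 326.5 effective patients per arm. For non-inferiority with 5% risk in both arms, SE = √(2 × 0.05 × 0.95/326.5) = 1.71 points. Power = Φ(5/1.71 − 1.96) = 83.4%. The plan states 83%, so the inputs are read correctly.

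**Step 2. SE of the interaction.** With 960 cancers, full inflation gives D = 1 + (960/24 − 1) × 0.01 = 1.39. Patients per arm are n₁ = 960*f*/(2D) in the subgroup and n₂ = 960(1 − *f*)/(2D) in the rest. The interaction is the difference between two risk differences, so

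SE² = Σ p(1 − p)/n over the four cells.

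Example: *f* = 50%, D = 1, all cells at 5%. Each cell has 240 patients and SE = √(4 × 0.0475/240) = 2.81 points.

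**Step 3. Power and mean significant estimate.** With t = δ/SE, P₁ = Φ(t − 1.96) and P₂ = Φ(−t − 1.96):

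- power = P₁ + P₂
- mean absolute significant estimate = [δ(P₁ − P₂) + SE(φ(1.96 − t) + φ(1.96 + t))]/(P₁ + P₂)

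In the example t = 1.78, power is 43%, and the mean is about 5 + 2.81 × 0.392/0.427 = 7.6 points, or 1.5 times the truth.

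**Step 4. True interaction of 5 points.**

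| Share | D | Cell risks | SE (points) | Smallest significant estimate (points) | Power | Mean significant estimate / truth |
|---|---|---|---|---|---|---|
| 50% | 1 | all 5% | 2.81 | 5.5 | 43% | 1.52 |
| 50% | 1 | one at 10% | 3.11 | 6.1 | 36% | 1.64 |
| 50% | 1.39 | all 5% | 3.32 | 6.5 | 33% | 1.73 |
| 50% | 1.39 | one at 10% | 3.67 | 7.2 | 28% | 1.89 |
| 10% | 1 | one at 10% | 5.55 | 10.9 | 15% | 2.74 |
| 10% | 1.39 | one at 10% | 6.55 | 12.8 | 12% | 3.20 |

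The rows with all cells at 5% understate the SE, since a 5-point interaction needs at least one different risk. They are kept as the favourable end of the range. In every row the smallest significant estimate exceeds 5 points.

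**Step 5. True interaction of 10 points** (one cell at 15%, the others at 5%, equal subgroups). With D = 1, power is 85%, the mean significant estimate is 10.9 points (1.09 times) and 41% of significant estimates lie below the truth. With D = 1.39 the figures are 72%, 11.9 points (1.19 times) and 30%.

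**Step 6. Aim 3 for contrast.** There are 32,000 patients. Assume a patient-level modifier that varies within sites and a true interaction of 0.14 SD. SE = √(2/(16,000*f*) + 2/(16,000(1 − *f*))), which is 0.022, 0.028 and 0.037 SD for shares of 50%, 20% and 10%. Power is above 99%, above 99% and 96%, with almost no overstatement.

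**The case against.** **A reader might infer that only exaggerated subgroup results can appear in this trial.** The documents do not support that. The rule covers the models of all aims, while the sentence about power stands in the Aim 1 text. Aims 3 and 4 plan on 32,000 patients, and step 6 shows that a patient-level modifier there can be tested with high power. Within Aim 1, step 5 shows 30% to 41% of significant estimates falling below a true 10-point interaction when subgroups are equal. Modifiers defined by site, such as care setting or region, are different: they rest on 24 clusters and have little power in any aim.

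**A reader might also add a false-positive rate to the charge.** With independent tests at 0.05, the six categories in the heterogeneity section give 1 − 0.95⁶ = 26% for one outcome, and the four factors in the Aim 1 text give 1 − 0.95⁴ = 19%. That comes from multiple testing. The reporting condition does not cause it and full reporting would not reduce it.

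**The plan has real safeguards.** Modifiers and direction are pre-specified, the Aim 1 analyses are labelled exploratory, and testing the interaction before opening subgroups is a common guard against over-reading. Nothing forbids reporting the interaction term itself or further estimates. These points limit misuse, but they do not commit the investigators to showing the missing estimates.

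**The arithmetic is approximate.** The planned primary model is hierarchical logistic regression, so the interaction would be tested on the log-odds scale. For modifiers that vary within sites, much of the clustering effect cancels. Both points are reasons to give a range, and the favourable end of that range still shows overstatement by half.

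**Conclusion.** The point holds as a reporting problem that bears most heavily on Aim 1. The plan states a rule that makes subgroup-level results depend on significance, in a setting it describes as underpowered. For the Aim 1 primary outcome, a true interaction of 5 points would pass in about 12% to 43% of trials and be overstated on average by a factor of about 1.5 to 3.2; otherwise its subgroup estimates would not be shown under the rule. The size depends on the assumed subgroup shares, cell risks, design effect and risk-difference scale.

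The overstatement shrinks as the true interaction grows and may be negligible for patient-level modifiers in Aims 3 and 4. The primary non-inferiority conclusion is not affected. This is a worthwhile improvement, not a threat to the trial.

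**What to change.** In the Subgroup Analyses/Heterogeneity of Treatment Effect section, replace the conditional clause with a commitment to report, whatever the interaction p-value:

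- the treatment effect and 95% confidence interval for every level of every pre-specified subgroup;
- the interaction estimate with its 95% confidence interval;
- the number of interactions tested.

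Align the Aim 1 text under H1c in the same way. For H2b, report the arm comparison with its interval at each survey time point, whether or not the treatment-by-time interaction is significant. Keep the exploratory label.

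The cost is a longer table or a forest plot. No new data, patients or design change are needed.
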